Efficacy Evaluations	
Expected Results and interpretation:
 
Our aim is to develop a panel of biomarkers and an algorithm for calculating a Cho status score that correlates well with measures of Cho pool size by isotope dilution. We will define the minimum set of biomarkers that provides >90% accuracy in predicting Cho pool size measured by isotopic dilution. We expect to see incremental declines in Cho status, as reflected in the panel of biomarkers. Results on the 100% diet should be similar to what we previously published. In the earlier studies, subjects were fed the 10% diet for a period of 2 to 7 weeks; in the proposed study, we feed 25%, 50%, and 100% (adequate intake) diets for two weeks (order randomly assigned) with 2 week washout periods in between. We expect that our results on the 25% & 50% diets will be less than those previously described; i.e. there will be smaller difference in the biomarkers than previously described. We expect that the 25% & 50% diets will show changes in Cho pool size and in biomarkers that fall between 100% and 10% values. Genotype will change the rate at which a diet treatment alters Cho pool size but will not affect whether our biomarker panel correlates with the pool size achieved. Thus, we do not have to power the study for genotype differences.

Pharmacokinetic Evaluations	N/A
Safety Evaluations	After each diet period a clinical chemistry panel will be run to assess potential liver and muscle damage. If any damage is noted after any of the dietary periods (liver damage = >1.5-fold increase in aspartate aminotransferase (AST) alanine transaminase (ALT) or muscle damage = >5-fold increase in creatine phosphokinase (CK)), affected subjects will follow the abnormal lab value protocol chart (See Appendix Figure 6). This will be reported to the IRB and the subject will be monitored and re-tested according to protocol and until AST/ALT and CK values return to normal.

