Statistical And Analytic Plan	(Aim 1, SubAim 1a,1b). Unsupervised principal component analysis will first be used to examine the clustering of samples from the diet periods, and to ensure that the QC pool replicates center in the samples from which they were derived. Supervised Orthogonal Partial Least Squares Regression (OPLS-R) will then be used to identify a panel of biomarkers, assign weight to each biomarker, and calculate a composite score to predict choline pool size. We will analyze all of the samples using OPLS-R to identify a panel of biomarkers that predicts choline pool size universally for all three diet periods (healthy men, pre- and post-menopausal women). We will also consider performing the analysis for each diet period separately in case the universal panel does not provide high accuracy in prediction. Variable Importance to Projection (VIP) score will be calculated based on the OPLS weights and the variability explained in OPLS-R. Biomarkers with VIP>1.5 will be considered the most important biomarkers responsible for prediction.

Pathway analysis will be performed using GeneGo metacore (Thomson Reuters, <https://portal.genego.com>) and QIAGEN's Ingenuity Pathway Analysis (IPA®, QIAGEN Redwood City, www.qiagen.com/ingenuity).

DATA AND SAFETY MONITORING PLAN [name] (PI), [name] MD, and study physician, [name] will monitor subject data for safety continuously throughout the study and as new subjects are recruited.

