People need to have a source of Cho: Cho has several important functions. It is (i) a source of methyl-groups needed to make the primary methyl donor, S-adenosylmethionine; (ii) a part of the neurotransmitter acetylCho; and (iii) a component of the major phospholipids in membranes (phosphatidylCho (PtdCho) and sphingomyelin)

(13). The Cho derivative, PtdCho is a main constituent of very low density lipoproteins (VLDL) and is required for VLDL secretion and the export of fat from liver (14). Cho also is important for normal fetal development (15, 16).

Cho is a required nutrient and in 1998, an Adequate Intake (AI) and a Tolerable Upper Limit (UL) for Cho was established (17). In 2016, the US Food and Drug Administration (FDA) set a Recommended Daily Intake (RDI) for Cho based on the AIs as part of the new Nutrition Facts label for packaged foods (published in the Federal Register on May 27, 2016; FDA-2012-N-1210-0875, Federal Register Number:2016-11867). The AI/RDI varies by age and gender, but is 550 mg/d in adult men and 425 mg/d in adult women (more in pregnant and lactating women).

Dietary Cho intake varies over a 3-fold range: There is a wide variation in Cho intake in the diet; in several human cohorts, Cho intake varies by approximately 3-fold – the US National Health and Nutrition Examination Survey (NHANES 2009-2012) data show that only 11% of adult Americans achieve the Adequate Intake level of Cho, with mean intake being 300 mg/day (10%ile being 200 mg/d; 90%ile being 500 mg/d) (2). Similar ranges of intake were reported in the Framingham Offspring Study (18), the Atherosclerosis Risk In Communities study (19, 20) and the Nurse's Health Study (21). Intake of Cho is even lower in low-income countries such as Jamaica and The Gambia (22, 23).

[figure not shown]

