Genetic variation influences risk for becoming Cho depleted: Single nucleotide polymorphisms (SNPs) in several genes related to Cho and folate metabolism alter the risk for developing organ dysfunction when people become Cho depleted (25, 35, 51, 52). PEMT (phosphatidylethanolamine-N-methyltransferase) catalyzes the formation of Cho moiety as part of PtdCho (53) and this pathway can reduce the amount of Cho that must be obtained from the diet (3). This gene is induced by estrogen; with maximum induction at the concentrations achieved in women during pregnancy (54). Women with the C allele of *PEMT* rs12325817 (74% of Caucasian women) are more susceptible to liver damage when consuming a low Cho diet (51, 55) because this allele abrogates estrogen-induced expression of the gene (56). Other *PEMT* SNPs also increase Cho requirement (rs4646343-A and rs3760188-A) (52). A number of other common SNPs in genes related to choline metabolism alter the requirement for Cho (25, 35, 51, 52, 57-59). Thus, similar dietary intakes may lead to very different Cho status, depending on genotype.

Given the narrow range for healthy intake of Cho, given the establishment of a RDI/AI for Cho to maintain health, given the 3-fold variation in dietary intake in the US, given the effects of common SNPs on the dietary requirement for Cho, and because plasma Cho concentrations do not adequately reflect status (see below), it is important that a good biomarker panel for assessing Cho status be established.

Potential biomarkers for Cho status: Self-reported dietary intake is very hard to measure accurately, and

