2.1 Primary Objective

Determine whether, in people, a choline status score based on measurements of a panel of biomarkers correlates well with measures of choline pool size as assessed using an isotope dilution method.

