3.1 Study Design

This is a crossover study wherein each subject will serve as their own control. Comparisons will be made between the low choline diet periods to the 100% choline diet at the beginning and end of the 6 weeks on the three dietary intervals (see Fig. 1, Appendix).

Screening: Before entry to the study the participants will be seen at the University of North Carolina Nutrition Research Institute Outpatient Clinical facility where a physical exam by a physician and a Clinical Chemistry panel will be performed to ascertain that they are healthy. Subjects will have mass resonance spectroscopy to measure Cho compounds in liver, and mass resonance imaging to assess fatty liver to validate the isotope dilution methodology and Fibroscan technology, respectively.

Intervention: Recruited subjects will be asked to fill out the Automated Self-Administered 24-hour Dietary Assessment Tool (ASA24) found on the NCI web site (<https://epi.grants.cancer.gov/asa24/>) for 3 days the week prior to the first diet intervention. This will estimate the choline intake level for subjects beginning the study. The week after screening, subjects will be placed on one of the three dietary choline levels (100%, 50%, and 25% - order randomly assigned) with a minimum 2 week washout between. On day 12 of each diet period, subjects will receive a 250mg bolus dose of the Cho delivered as Cho-d9 in order to estimate Cho pool sizes by isotope dilution (see Fig. 1, Appendix).

Follow-up: If the clinical laboratory data remain within normal values, this will conclude the subject's participation. If not, see section 4.3 (below).

Unscheduled Visits: Subjects may have to make unscheduled visits to pick up food if their freezer storage space is limiting.

3.2 Allocation to Treatment Groups and Blinding (if applicable):

All subjects will be randomly assigned to the order of the diet interventions. Investigators making metabolite, MRI, MRS, or Cho pool analyses will be blinded to diet assignments.

3.3 Study Duration, Enrollment and Number of Subjects:

The study lasts 10 weeks and a few days for each subject. We plan to enroll 150 subjects: 50 males, 50 pre-menopausal females, and 50 post-menopausal females. We will recruit an additional 30 subjects to account for drop out replacement, so the total number of subjects is 180.

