6.3 Statistical Methods

Statistical methods (Aim 1, SubAim 1a,1b). Unsupervised principal component analysis will first be used to examine the clustering of samples from the diet periods, and to ensure that the QC pool replicates center in the samples from which they were derived. This will enable the evaluation of the stability of the platform across the plate and between days for the signals which have not yet been assigned, to remove any signals that are too random and prevent the desired clustering, and to identify subjects who outlie from their perspective diet periods. Supervised Orthogonal Partial Least Squares Regression (OPLS-R) will then be used to identify a panel of biomarkers, assign weight to each biomarker, and calculate a composite score to predict choline pool size. When we applied Orthogonal Partial Least Squares Effect Projections (OPLS-EP) and Orthogonal Partial Least Squares Discriminant Analysis (OPLS-DA) to our previous data, we identified a panel of biomarkers and calculated a composite score that successfully predicted choline status (baseline or depletion) for both men and women (**Figure 1**). In this proposed study, we will use OPLS-R instead of OPLS-DA, because choline pool size is a continuous variable, while choline status in our previous study was a categorical variable. We will analyze all of the samples using OPLS-R to identify a panel of biomarkers that predicts choline pool size universally for all three diet periods (healthy men, pre- and postmenopausal women). We will also consider performing the analysis for each diet period separately in case the universal panel does not provide high accuracy in prediction. For the purpose of validation, we will not split samples into training and testing sets, as it reduces the number of samples used for model building. Instead, prediction error will be estimated using the Bootstrap method, which was found by recent studies as providing “nearly unbiased estimates of future model performance without holding back data when making the final estimates of model parameters” (101). Variable Importance to Projection (VIP)

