6.4 Sample Size and Power

Sample size estimation (Aim 1, SubAim 1a,1b). Similar to OPLS-DA, OPLS-R is a multivariate method for prediction. Different from hypothesis testing methods such as t-test or ANOVA, where sample size is determined by the power of rejecting null hypotheses when the alternative hypothesis is true, the sample size of OPLS-R is determined by its accuracy of prediction. In this study, we propose to recruit three groups of subjects (healthy men, pre- and postmenopausal women) with $n=60$ /group (estimated that $n=50$ /group will complete study). We plan to analyze all three groups together ($n=50*3=150$ subjects) to identify a formula for composite score that can predict choline pool size for all three groups. In case the universal score does not perform well, we will analyze each group ($n=50$ subjects) separately. Using our previous data with $n=44$ subjects, we successfully identified a panel of metabolites that can be used to predict whether a sample is taken at baseline or after choline deficient diet. As shown by the ROC plot, the area under curve was 98.77%, which indicates very high sensitivity and specificity (Figure 2). Our previous study indicates that there is a strong association between the panel of biomarkers and choline status even when the model was developed with a relatively small number of samples.

Sample size estimation (SubAim 1c). This analysis will first be applied to the *PEMT* SNPs (rs12325817-C; rs4646343-A and rs3760188-A) that are known to interact with the effect of dietary choline in women but not in men (24). This analysis serves to confirm the consistency between the performance of the choline status score and existing knowledge. Assuming the effect size of the diet \times genotype interaction is 0.6 (moderate effect), we

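### Aim 1 tests the choline score only across three assigned intakes; no planned analysis relates score to pool size among people on the same diet

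*Combined protocol and SAP*

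**What the plan says.** Section 1.1 gives several reasons for a biomarker panel. One is that intake does not fix status: "Thus, similar dietary intakes may lead to very different Cho status, depending on genotype".

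Section 2.1 sets the primary objective as whether the score "correlates well with measures of choline pool size as assessed using an isotope dilution method". It gives no threshold and no condition about diet. The synopsis (Efficacy Evaluations) adds a target: "We will define the minimum set of biomarkers that provides >90% accuracy in predicting Cho pool size measured by isotopic dilution". The accuracy measure is not defined.

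The design is a crossover in which "subjects will be placed on one of the three dietary choline levels (100%, 50%, and 25% - order randomly assigned"; every completer eats all three diets. (Section 8 still describes a fixed order, but the point below holds either way.) Section 6.3 will "analyze all of the samples using OPLS-R to identify a panel of biomarkers that predicts choline pool size universally for all three diet periods" and will estimate prediction error for that model by bootstrap. Diet is not a term in it.

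There is one fallback, in the synopsis and Section 6.3: "We will also consider performing the analysis for each diet period separately in case the universal panel does not provide high accuracy in prediction". The sentence before it follows the words for diet periods with a parenthesis listing men and pre- and postmenopausal women. Section 6.4 words the fallback as "In case the universal score does not perform well, we will analyze each group". Sex/menopause groups therefore appear to be meant, not diets.

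SubAim 1c (Sections 5.1, 6.2 and 6.3) fits a repeated-measures model with diet and genotype as fixed effects, once with the score as response and once with pool size.

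**The concern.** The assigned diet is expected to move both pool size and the biomarkers. Pooling the three diets therefore mixes two kinds of agreement: that which arises because both quantities follow the diet, and that which arises because people who are more depleted on a given diet have a worse score. The stated use, finding people with depleted stores, needs the second kind as well as the first.

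A score that reflects recent intake and nothing else would earn a pooled correlation from the first kind alone. It would also follow each person's own change from diet to diet, so a within-person analysis would not reveal the problem. The fallback would not either: it is only considered if the pooled panel disappoints, it seems to concern groups, and it would refit panels instead of examining the universal score at a fixed diet. If the pooled result looks good, no planned analysis shows which kind of agreement produced it.

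**Working it through.** **The plan's own figures.** Aim 1 has no power or precision figure. Its sample size (Section 6.4) rests on an area under the curve of 98.77% for telling baseline from depletion samples in 44 earlier subjects, which is itself a diet-recognition task. The 89.61% power belongs to the SubAim 1c interaction. It cannot be uniquely reproduced because the number analysed, sidedness and genotype split are not given, and nothing below depends on it.

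**Inputs.** Diets at 1, 0.5 and 0.25 of the recommended intake; 150 completers (50 in each of three groups). Assumption: mean pool size falls by D within-diet standard deviations from the 100% to the 25% diet, linearly in dose. The documents give no D, so a range is shown.

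**Perfect diet-only score.** Scaled positions of the diet means are (x − 0.25)/0.75 = 1, 0.333 and 0. Their mean is 0.444 and their variance is (0.309 + 0.012 + 0.198)/3 = 0.173. With within-diet variance 1, the between-diet variance is B = 0.173 D², and the pooled correlation is r = √[B/(B + 1)].

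**Imperfect recogniser.** Under equal-variance normality, an AUC of 98.77% corresponds to d = √2 × 2.248 = 3.18 between extreme diets. The share of score variance due to diet is then 0.173/(0.173 + 1/3.18²) = 0.636, so r is multiplied by √0.636 = 0.797.

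| D | B | B/(B + 1) | r, perfect diet-only | r, imperfect recogniser |
|---|---|---|---|---|
| 1 | 0.173 | 0.147 | 0.38 | 0.31 |
| 2 | 0.691 | 0.409 | 0.64 | 0.51 |
| 3 | 1.556 | 0.609 | 0.78 | 0.62 |
| 5 | 4.321 | 0.812 | 0.90 | 0.72 |

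If the diet means are equally spaced, the variance is 1/6 and r for a perfect diet-only score is 0.38, 0.63 and 0.77 at D = 1, 2 and 3. Within a diet, the perfect version is constant and explains nothing; the imperfect version has an expected correlation of 0 (simulated means −0.01 to +0.01).

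**Would the bootstrap expose it?** In simulated trials of 150 people on three diets, with the imperfect recogniser and resampling by participant, the optimism-corrected R-squared was 0.38 at D = 3 and 0.52 at D = 5. The uncorrected theoretical values are 0.622² = 0.39 and 0.719² = 0.52. The bootstrap corrects for overfitting, and this is not overfitting.

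**Would the accuracy target exclude it?** If the target means R-squared above 0.90, then B/(B + 1) = 0.90 requires B = 9 and D = √(9/0.173) = 7.2, so a diet-only score would almost certainly fail. If it means a correlation of 0.90, D of about 5.0 is enough. Section 2.1 sets no figure.

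**Can a within-diet check be estimated?** With 150 people per diet, Fisher's z gives 95% limits around r = 0 of tanh(1.96/√147) = ±0.16. Power (two-sided 0.05) is 69%, 87% and 96% for true within-diet correlations of 0.2, 0.25 and 0.3. With 50 people (one group on one diet) it is 56% at 0.3 and 83% at 0.4.

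**The case against.** **SubAim 1c is a same-diet validity check.** Section 5.1 (Genotyping) presents it as a test of the score and of the isotope measure at any given diet, and Section 6.4 uses the PEMT variants to confirm that the score behaves as existing knowledge predicts. A score reading only diet should show no genotype effect. A reader might infer that same-diet behaviour is never examined; that is too strong. What remains is that SubAim 1c is secondary, treats score and pool size as separate responses, and covers only differences linked to genotype. Section 10 also appears to postpone genotyping until a follow-on study is certain.

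**Correlation across degrees of depletion is the stated goal.** Section 2 says so, and Section 1.1 notes that self-reported intake is unreliable. A score that detects diet-induced depletion would therefore have real use. A reader might infer that a pooled success would mean nothing; the documents do not support that. The model is also trained on continuous pool size, not diet labels, and its candidates include markers of organ dysfunction.

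**The premise limits the size.** If status varies widely at a given intake, D is small, and a diet-only score reaches only 0.3 to 0.4 at D = 1. This stands.

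**Same-diet differences are not clean truth.** Section 5.1 defends the isotope method chiefly for changes between diet periods and concedes that new synthesis dilutes the label more in women with estrogen. Differences between people on one diet may reflect sex, body size or reference error. This stands, and it rules out making within-diet performance a pass/fail condition or adjusting for diet alone.

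**Conclusion.** The concern holds as a gap in what Aim 1 will report. It does not show that the score will fail or that pooling is wrong. A diet-only score would give a positive pooled correlation, about 0.38 to 0.78 for D from 1 to 3, which the bootstrap would leave standing. The size rests on an assumed D and on diet means roughly linear in dose. The accuracy target would exclude such a score only under a strict R-squared reading that the plan does not define.

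A reader might also infer that the pooled correlation is inflated by a calculable amount because the trial's intakes are spread more widely than the survey intakes in Section 1.1 ("mean intake being 300 mg/day (10%ile being 200 mg/d; 90%ile being 500 mg/d"). That does not follow. Intake is neither of the two variables being correlated, so a range-restriction formula does not apply.

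**What to change.** Keep the pooled analysis as planned. With the universal weights fixed, so not refitted by diet, always report beside it:

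- the score-versus-pool-size correlation on each of the three diets;
- the partial R-squared of the score adjusted for assigned diet (three levels) and sex/menopause group, with body weight added as a sensitivity adjustment;
- the reduction in prediction error over a model containing diet and group alone.

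Give all of these bootstrap intervals that resample participants, since each contributes three samples. Do not use them as a gate. If within-diet performance is near zero, limit the conclusion to tracking diet-induced depletion. Define the accuracy measure behind the 90% target, and correct the diet-period wording in the synopsis and Section 6.3 where groups are meant.

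The cost is plan wording and a few additional models on data already to be collected, with no new visits, samples or participants. The drawback is that within-diet figures will be lower than the pooled one and are further reduced by error in the isotope reference. The report should say so.

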1.2 Name and Description of Investigational Product or Intervention

Diets: The experimental diets, delivering 100%, 50% and 25% of the recommended intake of Cho (in all forms) (550 mg Cho/70 kg body weight/d), are identical except for the bread that we offer (Cho in the bread will be varied to deliver the desired Cho above that delivered by the base 25% Cho diet as described previously (1)). The base 10% Cho diet is composed of 0.8 g high biologic value protein/kg [current Recommended Dietary

Allowance (RDA)], with 30% kcal coming from fat and the remaining kcal from carbohydrate; diets are purchased commercial meals that have been measured for total nutritional values to acquire specific choline amounts for controlled choline intake. These diets were designed to bracket the range of dietary intake observed in several large published human population studies (18-23, 75). We have experience preparing and using diets with similar choline controls for more than 60 days per subject in our previously published studies (10, 24, 25, 51, 55).

Total food intake will be adjusted to be isocaloric (using snacks that contain minimal choline in any form) and to provide adequate intakes of macro- and micronutrients. All diets meet or exceed the Estimated Average Requirement for methionine plus cysteine, and the RDI for vitamins B₁₂, B₆, and folate. A multivitamin supplement (Kirkland Signature Daily Multi Vitamins and Minerals; Costco, Seattle, WA) provides vitamins and minerals at or above the RDI or Adequate Intake. Subjects will also be given a dietary supplement containing the RDI of magnesium and 1.5 times the Adequate Intake of calcium (Calcium Magnesium Complex; Vitamin Shoppe, North Bergen, NJ). We will use a 3-day diet menu of equivalent diets to allow for meal diversity. On the last 5 days of a diet period, subjects will consume 22% of their total Cho in the form of Cho chloride-(trimethyl-d9; 98%; Cambridge Isotope Laboratories, Tewksbury, MA, USA) replacing non-labeled Cho mole for mole in the bread. We will confirm total Cho content of diets by LC-MS/MS analysis of samples of duplicate food portions as previously described (1). Cho content and stability during storage of Cho in the bread will be separately determined.

Compliance with the diet plan will be assessed by having subjects bring back empty containers, by verbal check every week when new food is picked up, and by checking biomarker values and determining whether they deviate from gender-matched group mean data by more than 2 standard deviations. In addition, we will assess plasma and urine samples for presence of elevated riboflavin levels as a compliance biomarker, as riboflavin will be included in the dinner rolls used to supplement Cho intake.

